### **Control Dyads:**

[figure not shown]
The research assistant will approach all eligible patients in the clinic to inform them of patient-caregiver study (**Attachment U: RA Talking Points**). Interested patients will be asked to identify a caregiver to participate, however patients can participate in the study regardless of caregiver participation. The dyad will provide consent (**Attachment F: Informed Consent – Control**) (eConsent). At the completion of the control participant's 8-week study period, the dyad will complete the post-period survey (**Attachment C – Post Treatment Survey Patient and Attachment D: Post Treatment Survey Caregiver**) based on their stated format

preference determined during consent - in clinic, electronically or mailed (**Attachment O: Initial Post- Treatment Survey Patient Communication – Control** and **Attachment P: Initial Post Treatment Survey Caregiver Communication – Control**). Patients and/or caregivers that do not complete the survey in one week will receive a reminder to complete the survey (**Attachment Q: Reminder- Post Treatment Patient Communication – Control** and **Attachment R: Reminder – Post Treatment Caregiver Communication – Control**). Three total follow-up attempts will be made to non-responders approximately one week apart; attempts will be made if no data or incomplete data are received with the goal of obtaining completed surveys. Once the study team receives the completed survey, the patient and caregiver will each receive a \$25 gift card. The gift card will be mailed to each individual (**Attachment T: Compensation Letter**). Participants who do not receive a copy of their consent form at the time of consent will be mailed a copy of their consent form for their records (**Attachment BB: Consent Form Letter**).

The caregiver identified by the patient may not be present for appointments (e.g., caregiver resides out of state). In such cases, enrollment in the study will need to be coordinated over the phone and by email. The study staff will ask the patient to speak with the identified caregiver about their interest in participation. If interested, the study team will ask the patient to provide the caregivers name and contact information. The study team will then reach out to the caregiver to explain the study in more detail and determine their interest in participation (**Attachment V: RA Script**). If the caregiver is interested in participating, the RA will explain to the caregiver that they will receive an e-mail to provide their consent to participate (**Attachment M: Initial Recruitment Email Caregiver – Control**). If after one week the caregiver does complete their consent, a reminder will be sent to the participant (**Attachment N: Reminder –Recruitment E-mail Caregiver – Control**). Once the patient reaches the end of their study period, the caregiver will receive request (**Attachment P: Initial Post-Treatment Survey Caregiver Communication – Control**) to complete the survey. In one week, a follow-up will be sent to non-responders (**Attachment R: Reminder – Post Treatment Survey Caregiver Communication – Control**). Three total follow-up attempts will be made to non-responders approximately one week apart; attempts will be made if no data or incomplete data are received with the goal of obtaining completed surveys. Once the study team receives the completed survey, the caregiver will receive a \$25 gift card. The gift card will be mailed to each individual (**Attachment T: Compensation Letter**)

**Providers:** Providers in the treatment site will be asked to participate in a 30-minute interview (**Attachment Y: Physician Interview Guide** with the study team at the post-period. The interview will occur in a private setting either in an office or conference room. Providers will identify the best time to meet with the study team to participate in the interview. Participation will not interfere with the delivery of patient care, perhaps brief one-on-one interviews will be held in parallel or adjacent to regularly scheduled administrative meetings or meal times, strategies that reduce provider burden. In addition to the interview, application metrics and demographic data will be collected on all providers. See section 4.8.1 for more details.

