This study is characterized as an exploratory evaluation as the design limits the generalizability of findings and these findings will be biased in several ways. First, the treatment clinic and clinicians have been intimately involved in the development and implementation of the FCA. This factor likely influences clinician adoption of the FCA in care and could be limiting factor in other settings where FCA may be tested. Additionally, sites were conveniently chosen and site-level factors may bias study findings. The administration of the study sites is centralized to infer some consistency with operational procedures however this is a limiting factor in this exploratory evaluation. Quality and performance metrics are not routinely collected in these outpatient settings. In the absence of system-level data to describe variation in care, the study will depend on study questionnaires to evaluate quality and performance, which is a limiting factor as the perspective is contained to the study participants rather than the aggregate patient-population at each site. Secondly, a convenient sample of patients receiving care at the study clinics will be recruited into the study on a first-come, first serve basis and without random assignment to treatment or control groups. Additionally, Case Dyads must enroll in MyGeisinger patient portal to use FCA and although not required for the study, we will encourage Control Dyads to enroll in MyGeisinger patient portal to minimize bias related to health literacy using technology. Another potential bias is that some caregivers may reside out of state and this distance may impact the quality of their relationship with the patient; every effort will be made to match Case and Control Dyads with similar spatial situations but this may be prohibitive given the project timeline. These factors limit the assumption that any observations associated with FCA are related to the treatment use as variation in patient factors or the quality of care at clinics may account for observed associations. Potential participants (patients) are reasonably expected to receive an intense, brief oncology care with multiple appointments thus offering the opportunity to measure the impact of FCA use. Dyads will not be randomly assigned to treatment or control but offered standard of care per the clinic site. The study team will provide hands-on technical assistance to Case Dyads and associated clinicians to facilitate implementation and observe key learnings. Changes from baseline to post-study period will be evaluated within the Case Dyads, but given the severity of the condition and brief study period, the project team expects to observe greater differences in post-study period indicators between Case Dyads vs. Control Dyads.

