The caregiver identified by the patient may not be present for appointments (e.g., caregiver resides out of state). In such cases, enrollment in the study will need to be coordinated over the phone and by email. When this occurs and as possible, the study team will match Case Dyads to Control Dyads who have remote caregivers, but given the logistics of enrolling Case patients, then Case caregivers, matching and recruiting Control patients, and then recruiting Control caregivers in the brief study period, this may be difficult to operationalize and therefore be a source of bias as the Dyads' situations differ by distance. The study staff will ask the patient to speak with the identified caregiver about their interest in participation. Once the study team receives confirmation from the patient, the RA will ask the patient to provide the caregivers name and contact information. The study team will then reach out to the caregiver to explain the study in more detail and determine their interest in participation (**Attachment V: RA Scripts**). The RA will facilitate the applicable MyGeisinger and Proxy Access (**Attachment S: Remote Caregiver Letter**) and send an e-mail to the caregiver to consent and complete the baseline survey (**Attachment G: Initial Recruitment Email Caregiver – Case**). Follow-up will be made in one week if the caregiver has not consented or completed the baseline survey (**Attachment H: Reminder – Pre-Treatment Caregiver Communication – Case**). Three total follow-up attempts will be made to non-responders approximately one week apart; attempts will be made if no data or incomplete data are received with the goal of obtaining completed surveys. Once the study team receives the completed survey, the caregiver will receive a \$25 gift card. The gift card will be mailed to each individual (**Attachment T: Compensation Letter**).

Once consent is obtained, the baseline survey is complete and all applicable MyGeisinger and proxy access has been set up, the RA will call the caregiver to activate them in FCA intervention, offer and provide technical assistance, and confirm that the participating caregiver has at least a basic level of comfort with the FCA (**Attachment V: RA Scripts**)

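### Remote Control caregivers get one consent reminder, with its condition misprinted, against up to three follow-ups for remote Case caregivers, so the groups may differ in caregiver type

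*Combined protocol and SAP*

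**What the plan says.** Section 4.5 sets out separate enrolment steps for caregivers who cannot attend the clinic.

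- **Case Dyads.** The remote caregiver receives one e-mail asking for both consent and the baseline survey. Then: "Follow-up will be made in one week if the caregiver has not consented or completed the baseline survey". The next sentence adds: "Three total follow-up attempts will be made to non-responders approximately one week apart", and explains that "attempts will be made if no data or incomplete data are received with the goal of obtaining completed surveys".
- **Control Dyads.** The remote caregiver receives a recruitment e-mail (Attachment M). Then: "If after one week the caregiver does complete their consent, a reminder will be sent to the participant" (Attachment N). This paragraph also provides three follow-up attempts, but they come after the sentence that begins "Once the patient reaches the end of their study period, the caregiver will receive request", so they concern the post-period survey.

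Section 4.3 has the team recruit a replacement dyad in either group when the caregiver does not enrol, and removes Case patients without a caregiver from the analyses. The formal matching factors there are patient characteristics only: sex, age category, histology and stage.

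On caregiver distance, section 4.1 says that "every effort will be made to match Case and Control Dyads with similar spatial situations", while warning that the timeline may not allow it. Section 4.5 says that, as possible, "the study team will match Case Dyads to Control Dyads who have remote caregivers".

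**The concern.** There are two separate defects. The first is a wording error: the Control reminder is triggered by the opposite of what is meant. The second remains after that correction: the written effort to bring in a remote caregiver differs between the groups.

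The second matters because caregiver enrolment decides which dyads are analysed. If the team stops earlier with remote Control caregivers, more of them will be replaced, possibly by dyads with a local or quicker caregiver. Sections 4.6 and 4.8.1 average patient and caregiver scores within each dyad and compare the groups, and also compare caregivers directly. A difference in caregiver type would therefore feed into the primary comparison.

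The plan has little means of seeing or correcting it. Controls have no baseline survey (section 3.3), the between-group tests are univariate (section 4.8.1), and the caregiver data list in section 4.8.1 has no remote/local or distance item. The survey contents are not shown, so such a question may exist there.

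**Working it through.** The plan states no figure that depends on this point, so there is nothing to reproduce. The check is a comparison of the text, followed by an illustration.

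**Text comparison for a remote caregiver**

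| | Case | Control |
|---|---|---|
| Trigger at one week | consent or baseline survey missing | consent completed (as printed) |
| Follow-ups at enrolment stage | 3, about a week apart | 1 |
| Stated aim of the three attempts | completed surveys, in a combined consent and survey request | completed post-period survey only |
| Steps for this group only | portal proxy access, baseline survey | none |
| If caregiver does not enrol | dyad replaced | dyad replaced |

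The Case attempts are described as aimed at surveys. They also reach non-consenters, because the trigger names consent and a caregiver who has not consented has returned no data.

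**Illustration.** Inputs from the documents, with the 'not' restored: k = 4 contacts for Case (initial e-mail + 3), k = 2 for Control (initial + 1), 25 dyads per group. Assumed, because the documents do not give them: consent probability per contact p from 0.2 to 0.9, constant and independent across contacts; share r of caregivers who are remote from 10% to 30%; all local caregivers consent. Case-only hurdles are left out.

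Consent: c = 1 − (1 − p)^k. Expected remote dyads among 25: 25·r·c / (r·c + 1 − r).

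At r = 20% (gaps taken before rounding):

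| p | Case consent | Control consent | Case remote dyads | Control remote dyads | Gap |
|---|---|---|---|---|---|
| 0.2 | 59% | 36% | 3.2 | 2.1 | 1.2 |
| 0.3 | 76% | 51% | 4.0 | 2.8 | 1.2 |
| 0.5 | 94% | 75% | 4.7 | 3.9 | 0.8 |
| 0.7 | 99% | 91% | 5.0 | 4.6 | 0.3 |
| 0.9 | 100% | 99% | 5.0 | 5.0 | 0.0 |

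The largest gap on the whole grid is at p = 0.2, r = 30%: 5.0 − 3.3 = 1.7 dyads. At p = 0.9 it is close to zero for every r.

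**Effect on a score.** If remote and local caregivers differ by D points, the bias in the caregiver comparison is D times the difference in remote share. At the largest gap the shares are 0.202 and 0.134, so the bias is 0.068·D. In the dyad mean it is half that, 0.034·D, if patient scores do not depend on caregiver distance.

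**With equal follow-up.** k = 4 in both groups, and the modelled gap is zero for every p and r. Differences from proxy access, the baseline survey and the enrolment sequence would remain.

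**The case against.** A reader might infer that, as printed, Control caregivers who have not consented would never be reminded. The documents do not support that. Attachment N is titled a recruitment reminder, the parallel Case sentence has the negative, and reminding someone who has already consented serves no purpose. It is a slip to correct, and no effect size should be built on it.

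A reader might also infer that the groups will differ, with hard-to-reach caregivers kept among Cases and lost among Controls. That is too strong, for four reasons:

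- Replacement applies in both groups.
- Case caregivers must obtain proxy access and complete a baseline survey, which could lose remote caregivers from the Case group. The net effect could be nil or reversed.
- The remote caregiver has discussed the study before the e-mail is sent; for Controls it goes only to those who are interested. Consent per contact may therefore be high, where the gap vanishes.
- The Control text does not say that one reminder is the maximum, and Attachments N and V, which might say more, are not available.

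Section 4.2.1 also expects, from Phase II, that all patients enrolling as dyads will name a caregiver who consents. This carries limited weight. Phase II had 12 dyads in one clinic, the figure is not specific to remote caregivers, and the same section plans for 65 patients against 50 caregivers, allowing 15 patients without one.

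Finally, bias by distance is already disclosed: section 4.5 says of matching on it that "this may be difficult to operationalize and therefore be a source of bias". That stands, but the disclosure attributes the bias to enrolment logistics and a short timeline. Unequal follow-up is a further cause, and one the team controls. Some of the extra Case effort reflects an extra task, but that does not require fewer consent reminders for Controls.

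**Conclusion.** The point holds in limited form. The Control consent reminder has a dropped 'not'. Once that is corrected, the written follow-up at the enrolment stage is still three for remote Case caregivers and one for remote Control caregivers. With replacement of dyads whose caregiver does not enrol, the groups **may** differ in their share of remote or slow-to-respond caregivers, which adds an undisclosed and avoidable contributor to the distance bias that the protocol names.

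The reminder effect alone is between about 0 and 1.7 dyads of 25. This rests on the assumed remote shares and consent rates and on independent contacts, none of which the documents supply. The net direction cannot be determined, because the Case-only steps are not quantified.

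Severity is minor. The study is exploratory and non-randomised, its tests are declared descriptive, and section 4.1 already acknowledges that site and patient differences may account for what is observed. The case for acting is that the remedy is cheap.

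**What to change.** 1. In section 4.5, Control Dyads, insert the missing 'not' so that the reminder goes to caregivers who have not completed consent.
2. Use one consent follow-up rule for remote caregivers in both groups: up to three attempts, about one week apart. State that a dyad is replaced for caregiver non-enrolment only after those attempts are used up or the caregiver declines.
3. Record in REDCap, for every caregiver approached in either group, the number of contact attempts and whether the caregiver is remote or local. Report the remote share by group beside the main comparison.
4. Add unequal enrolment steps, including the Case-only proxy access and baseline survey, to the limitations in section 4.1.

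The cost is a few sentences, two data fields and up to two more e-mails (3 − 1) per remote Control caregiver. Some Control Dyads would take about two weeks longer to enrol or be replaced, within a planned seven-month recruitment period. The change does not remove differences due to the Case-only steps; item 3 would let any remaining imbalance in remote share be seen.

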#### 4.5.1 Study Flow Diagram

## 4.6 Primary Question

The primary endpoint will be difference in quality and performance metrics at the post-period associated with FCA **exposure**, evaluated between the Case Dyads and Control Dyads.

Aggregate means will be calculated for dyads and compared between groups. Sensitivity analyses may stratify these results by low-moderate-high FCA use. FCA exposure is designed to impact care coordination, patient satisfaction, patient and caregiver quality of life, perceived involvement in care, and symptom management, all quality indicators, over standard of care in control clinic sites where care coordination is less efficient, labor-intense, and often frustrating to patients and caregivers. Additionally, the Consumer Assessment of Healthcare Provider Survey, performance metrics, for Cancer Care and Health Information Technology scores for FCA users vs. controls is expected to be greater as controls would have standard of care with no additional enhancements and could utilize MyGeisinger portals.

Theoretical Domain	Parameter of interest operationalized	Perspective	Data sources or location
Quality of Care	
Patient Satisfaction with Service Quality Hospital operations and services; physicians and staff; endorsements for others
 
Family Satisfaction with Advanced Cancer Care Information giving, availability of care, physical care, psychosocial care
	Patient Caregiver	
Patient Survey Attachment A and C: Pre and Post Survey
 
Caregiver Survey Attachment B and D: Pre and Post Survey

Patient-Caregiver Outcomes	
Quality of Life Patient's functional scales, symptoms, financial impact and global health and quality of life ratings
 
Caregiver's own state, relationships, outlook, patient condition, finances, environment
 
Caregiver Burden Personal impact, other family members, medical issues, concerned about loved one
 
Clinical Outcomes Survival, remission, exacerbation, MD Anderson Symptom Inventory
	Patient Caregiver Caregiver Patient	
Patient Survey Attachment A and C: Pre and Post Survey
 
Caregiver Survey Attachment B and D: Pre and Post Survey
 
Caregiver Survey Attachment B and D: Pre and Post Survey
 
Epic EHR See section 4.8.1

Coordination of Care	Coordination of Care Establish accountability and negotiate responsibility; communication; information transfer; proactive plan of care; monitoring; support of patient and family self-management goals; teamwork focused on coordination	Patient-Caregiver	Patient and caregiver surveys  Attachments A-D: Patient and Caregiver Pre and Post Survey
	Coordination of Care Adoption of FCA Communicate, monitoring, patient- and caregiver- centered care, efficient, timely	Health Care Provider	Provider Interview Attachment Y: Physician Interview Guide
	Coordination of Care Health care utilization (scheduled vs. missed)		Epic EHR and Aria

	appointments, hospital admissions, ED visits), costs	Health System Representative	See section 4.8.1
	
Adoption Proportion of patients and families adopting and using app
	Health System Representative	
Epic patient lists, recruitment records, and FCA usage data
 
Patient Survey Attachment A and C: Pre and Post Survey
 
Caregiver Survey Attachment B and D: Pre and Post Survey

Demographics	
Collection of standard demographics variables
	
Patient-Caregiver Health Care Provider
	
Patient Survey Attachment A and C: Pre and Post Survey
 
Caregiver Survey Attachment B and D: Pre and Post Survey
 
Epic HER See section 4.8.1
 
FCA Metrics See section 4.8.1
 
Human Resources See section 4.8.1

## 4.7 Secondary Question

The secondary question, how does FCA **use** impact quality indicators will be evaluated as a change in these endpoints across two points in time, baseline and post-survey. Change in these quality and performance metrics among the Case Dyads from baseline to post period will be evaluated. These observations may be enriched with qualitative feedback from the healthcare providers that participate in interviews after all Case Dyads have completed their 8-week study period. This question relates to use of FCA only and therefore only data from the users of FCA will be used to address this question, e.g., Case Dyads and healthcare providers of the Case patient-participants. This exploratory evaluation aims to describe how the use of FCA may impact quality indicators. Future studies may use these findings to design more rigorous studies that evaluate or test the use of FCA on quality indicators.

## 4.8 Statistics

Biostatistics Core will perform the statistical analyses.

### 4.8.1 Statistical Analysis Plan

The study team will describe quality and performance indicators observed among study participants and evaluate associations between 1) difference in quality of care (satisfaction, quality of life, burden, coordinated care) associated with FCA exposure (Case Dyads vs. Control Dyads, Post-Treatment Surveys only); and 2) change in quality of care (satisfaction, quality of life, burden, coordinated care) associated with FCA use (Case Dyads Pre-Treatment Surveys vs. Post-Treatment Surveys).

Case Dyads and Control Dyads demographic and clinical information and survey responses will be fully described using frequencies and percentages for categorical variables and mean and standard deviation or median and interquartile range for continuous variables distribution dependent. To evaluate the difference in quality of care associated with FCA **exposure** (Case v. Control) will be evaluated using chi-square test, t-tests and non-parametric univariate tests distribution dependent. Mean patient and caregiver scores will be calculated for each dyad and compared between groups. Sensitivity analyses may stratify by level of FCA use (low-moderate-high) per dyad and opportunity time for FCA exposure. Case to Control patient analyses and Case to Control caregiver analyses will also be performed to detect role-level differences in perceptions of quality and performance associated with FCA exposure. To evaluate the association of the change in quality of care associated with FCA **use** difference in response between pre- and post- surveys paired t-test or ANCOVA depending on data type and distribution. Within Case Dyads, patient means will be compared with caregiver means to detect difference in quality and performance perceptions based on role.

All statistical analyses will be performed using SAS v9.4 (SAS Institute, Inc., Cary, NC, USA). All statistical tests are meant to be descriptive since this is purely an exploratory analysis.

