***Observe quality and performance indicators among usual oncology care in similar patient-caregiver population to compare with cases.*** From non-treatment sites, identify, recruit, consent, and enroll persons with lung cancer (newly diagnosed or recent recurrence of disease) and their caregivers into the evaluation study. Recruitment will continue until 25 patients and 25 caregivers are enrolled (Control Dyads). Electronic health records for patients (appointment, clinical, and patient-reported data such as the M.D. Anderson Symptom Inventory that is standard of care) and study questionnaires will be used to evaluate quality and performance indicators however, questionnaires will be fielded at the post-period only. Non-treatment sites will not provide FCA as standard of care and function as control sites. These sites will include Geisinger Wyoming Valley in Wilkes-Barre, PA (“GWV”), and Geisinger Community Medical Center in Scranton, PA (“GCMC”). A case-matched controlled design will be used to evaluate differences in quality and performance indicators between groups at the post-period only.

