#### Evaluate how Use of FCA may Impact Quality

The **second propose this project** is to evaluate how *use* of the FCA may impact quality indicators associated with oncology care. In this exploratory evaluation study, we aim to evaluate whether quality indicators change with exposure to FCA, thus pre-post difference within the Case group is an appropriate study design to answer this question or purpose. Future studies may use these exploratory evaluation findings to more rigorously evaluate or test

between group differences using appropriate study designs. Case Dyads will provide baseline and post-surveys.

NOTE: Throughout the protocol and IRB application we will refer to the study as the *Exploratory Evaluation of Family Caregiver Application*. In the consent form and other patient facing materials, we will abbreviate the project title and description to the *Care Coordination in Oncology Study*.

Also, the data analyst described throughout the proposal will serve in two roles 1) as a data analyst for research activities such as patient eligibility lists, recruitment reports, reporting needs, etc. and 2) as a data broker to maintain the application. The data analyst will be listed as research support staff in the IRB application given the research role.

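### The secondary question on FCA use is answered by the baseline-to-post change in Case Dyads, a contrast with no named use variable and no Control baseline, so it describes the 8-week course rather than use.

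*Combined protocol and SAP*

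**What the plan says.** The protocol separates two purposes: exposure (Case v. Control at the post-period) and use (within Case Dyads).

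**The use question.**
- Section 4.1, under *Evaluate how Use of FCA may Impact Quality*, justifies the design by whether indicators change with exposure, and concludes: "thus pre-post difference within the Case group is an appropriate study design to answer this question or purpose".
- Section 4.7 says that use and how it may "impact quality indicators will be evaluated as a change in these endpoints across two points in time, baseline and post-survey". It adds: "This question relates to use of FCA only and therefore only data from the users of FCA will be used to address this question". Case Dyads and the providers of Case patients are given as the example of users.
- Section 4.8.1 states the contrast as "change in quality of care (satisfaction, quality of life, burden, coordinated care) associated with FCA use (Case Dyads Pre-Treatment Surveys vs. Post-Treatment Surveys" and the test as "difference in response between pre- and post- surveys paired t-test or ANCOVA depending on data type and distribution". No ANCOVA terms are given.

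**Where level of use appears.**
- Section 4.6: "Sensitivity analyses may stratify these results by low-moderate-high FCA use". The results meant there are the Case v. Control results.
- Section 4.8.1: "Sensitivity analyses may stratify by level of FCA use (low-moderate-high) per dyad and opportunity time for FCA exposure". This comes before the pre-post sentence and is neither linked to the pre-post analysis nor barred from it. Neither place gives a metric or cut-points.
- The endpoint table in section 4.6 has an Adoption row, the proportion of patients and families taking up and using the app, drawn partly from usage data.
- The data elements in section 4.8.1 list log-on dates, features accessed and view counts for patients and caregivers.

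**Controls.** Section 3.3 (Specific Aim 3): "questionnaires will be fielded at the post-period only".

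**The concern.** A question about use needs a contrast in which use varies. Here only time varies. No minimum use is set, and the only stated removal from the Case analysis is for patients without a caregiver-participant (section 4.3). A dyad that hardly logs on therefore appears to count the same as a daily user.

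The interval is also not neutral. Under section 4.2.2 patients enter before chemotherapy or radiation starts or up to 27 days into it. Section 4.1 expects intense, brief care with many appointments. Under section 4.4.1 the post survey may come 1 to 2 weeks after that care ends. Quality of life, burden and satisfaction may well change over such a period whether or not the app is opened, and without a Control baseline nothing estimates that change.

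Followed as written, the plan would report change over the treatment course as change associated with FCA use. Section 4.7 expects future studies to be designed from these findings, so the label matters.

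**Working it through.** **1. The plan's own count.** The documents give no power, effect size or SD. The only figure to reproduce is the number of Case Dyads (section 4.2.1):
- 153 × 0.5 = 76.5, rounded to 77
- 77 × 0.37 = 28.5, given as 28
- 28 × 0.90 = 25.2, given as 25

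This reproduces. If instead 25 enrol and 90% complete, 25 × 0.90 = 22.5, about 22. Section 4.8.2 says 50 per group, so n = 22, 25 and 50 are all shown.

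**2. What the contrast estimates.** Mean pre-post change = course change + FCA effect. There is one equation and two unknowns, and no Control change to supply the second. This holds at any sample size and needs no assumed figure.

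**3. Illustration of the size.** Assumptions: scores in SD units, two-sided 5% level, pre/post correlation r, course change d unrelated to use, no FCA effect. The SD of the change is √(2(1−r)), so the standardised change is d/√(2(1−r)) and the noncentrality is that value × √n. For r = 0.5, d = 0.5, n = 25: 0.5/1 × 5 = 2.5, which gives 67%.

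| n | d = 0.3, r = 0.5 | d = 0.5, r = 0.5 | d = 0.5, r = 0.7 |
|---|---|---|---|
| 22 | 27% | 61% | 82% |
| 25 | 30% | 67% | 87% |
| 50 | 55% | 93% | 99% |

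The 95% CI half-width of the mean change is t × √(2(1−r)/n). At r = 0.5 and n = 25 this is 2.064 × 0.2 = 0.41 SD. At n = 22 it is 0.44 and at n = 50 it is 0.28. More dyads measure the same mixture more precisely.

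**4. A contrast that contains use.** The model is post score on pre score plus use, fitted to Case Dyads (simulation, 10,000 runs per scenario, r = 0.5).
- Use unrelated to outcome: the slope rejects in about 5% at each n, including with a course change of 0.5 SD.
- Partial correlation 0.5 and zero mean change: the slope is found in 67%, 73% and 96% (n = 22, 25, 50). The paired t-test stays at about 5%.
- Partial correlation 0.3: about 26%, 31% and 57%.

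The mean change and the slope thus answer different questions.

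**5. Limits of that slope.** The Fisher-z interval is tanh(atanh(r) ± 1.96/√(n−4)), with the pre score as covariate. For r = 0.5 and n = 25: 0.549 ± 0.428, which gives 0.12 to 0.75. At n = 50 it is 0.25 to 0.68. For r = 0.3 and n = 25 it is −0.12 to 0.63.

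Now let use have no effect, but let unmeasured severity correlate c with both use and the post-score residual. The induced partial correlation is c × c, so 0.25, 0.36 and 0.49 for c = 0.5, 0.6 and 0.7. The slope then rejects in about 22%, 42% and 71% at n = 25, and about 42%, 73% and 96% at n = 50.

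**The case against.** **Section 4.1 frames the purpose as change with exposure, a before-after question; a dose-response reading is the reviewer's.** This stands in part. But the protocol sets use apart from exposure as a second purpose and then justifies the second in terms of the first, so the inconsistency is its own.

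**The ANCOVA may already be the right model.** In a single group, ANCOVA needs a further term, and level of use is a natural one. Section 4.8.1 also mentions opportunity time. This stands as far as it goes: the plan does not exclude a use term. It does not name one either, and a paired t-test alone would satisfy it.

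**Use is analysed elsewhere.** True. A reader might infer that logged use is ignored, but the Adoption endpoint uses it and the optional stratification could. Adoption, however, is a proportion of users and does not relate use to change in outcomes.

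**The limits are disclosed.** Section 4.1 admits patient and clinic biases, and it expects larger between-group than pre-post differences given disease severity and the short period. Sections 4.8.1 and 4.8.2 call the tests descriptive. This lowers the stakes. Severity is mentioned there to explain which differences to expect. The treatment course is not named as a rival explanation of the pre-post change, and the design is still called appropriate.

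**The percentages in step 3 are ordinary paired-test power under assumed inputs.** Correct. They illustrate the point and the argument does not depend on them.

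**Conclusion.** The concern holds in this form: the secondary question on use is answered by a one-group change over time, with no use variable named and no Control baseline survey. The mean change is a mixture of treatment course and any FCA effect, whatever the sample size.

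The size shown (67% at n = 25 for a 0.5 SD course change, 30% for 0.3 SD) rests on assumed drift and a pre/post correlation of 0.5. The documents give neither.

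Three stronger readings are not supported:
- The 67% is not a false-positive rate. The paired t-test is valid for the mean change, and what fails is the label put on it.
- The plan makes no confirmatory claim. It describes, and defers testing to later studies.
- That non-users are kept in the analysis is an inference from the absence of a threshold and from Case Dyads being given as the example of users. The plan does not state it.

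The harm is a mislabelled description. It should be corrected because it concerns a named study question and the correction is cheap.

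**What to change.** In section 4.1 (*Evaluate how Use of FCA may Impact Quality*), 4.7 and 4.8.1:

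1. Report the mean pre-post change with its 95% CI as a description of the 8-week course in Case Dyads, not as an effect of or association with FCA use. Say that the treatment course is an alternative explanation. Keep the words use and exposure distinct throughout.
2. Write out the ANCOVA: post score on pre score plus one pre-named logged-use metric per unit of opportunity time (for example, log-on days per week since FCA activation), within Case Dyads. Fit it for a short pre-named list of outcomes, separately for patients and caregivers. Report slopes with 95% CIs as associations only.

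**Cost.** Wording, and a few regressions on data already collected; no new visits or surveys. It is several slopes rather than one. Satisfaction, quality of life and coordination for patients, and the same plus burden for caregivers, would make seven. If these were independent and all null, the chance of at least one p<0.05 would be 1 − 0.95^7 = 30%, hence the short list and the emphasis on intervals. The slopes will be imprecise at 25 dyads. Because use is self-selected and may track severity, they must not be read as effects (step 5).

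Separately, reconcile 25 dyads per group (sections 3.2, 3.3, 4.2.1, 4.3 and 4.4.2) with 50 (section 4.8.2). The precision of both analyses depends on it.
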